**Official Title of the Study: Behavioral Effects of Drugs: Inpatient (31)**

**NCT Number: NCT02522325**

**Document Date: July 2, 2015**

## 1. BACKGROUND

Cocaine (COC) addiction is an unrelenting public health concern. Behavioral therapies are effective for reducing COC use. However, many patients enrolled in behavioral therapy programs are unable to achieve significant periods of abstinence suggesting other strategies like pharmacotherapy are needed. An effective medication has not been identified for COC dependence despite being a high priority for the National Institute on Drug Abuse for nearly 30 years and extensive efforts by the scientific and treatment communities.

COC binds to monoamine transporters (i.e., dopamine [DA], norepinephrine [NE] and serotonin [5-HT]) and prevents their reuptake into the presynaptic terminal. The results of preclinical studies have shown that monoamine releasers attenuate the reinforcing effects of COC. The results of human laboratory studies also suggest monoamine releasers (i.e., d-amphetamine) attenuate the reinforcing effects of COC although the effects are small in magnitude and dependent on the methods used to assess drug reinforcement. The results of clinical trials that tested monoamine releasers for COC abuse are mixed.

Monoamine releasers vary along a continuum from DA/NE selective to 5-HT selective. Theoreticians have postulated that the 5-HT/DA releasing ratio is a critical determinant of the efficacy of a monoamine releaser to attenuate the reinforcing effects of COC. Compounds with intermediate 5-HT/DA release ratios (i.e., 30-40) have been the most effective and specific for reducing COC taking. For example, methamphetamine (5-HT/DA ratio = 31) completely and specifically eliminated responding for COC in monkeys. Consistent with these findings, methamphetamine dramatically reduced COC use in a clinical trial. d-Amphetamine had similar but less robust effects, possibly due to its higher 5-HT/DA release ratio (i.e., 71). Use of amphetamines for managing COC use disorders has met with reluctance due to high abuse and diversion potential. Compounds with a desirable 5-HT/DA releasing ratio and reduced abuse potential need to be tested for COC dependence.

Phendimetrazine (PHEN), a Schedule III medication under the Controlled Substance Act, is indicated for treating obesity. After oral administration, PHEN is converted to phenmetrazine, which is largely responsible for its behavioral and neuropharmacological effects. Consistent with the notion that compounds with intermediate 5-HT/DA release ratios selectively attenuate the reinforcing effects of COC, phenmetrazine (5-HT/DA ratio = 37) completely eliminated COC-maintained responding in monkeys. Recent research with PHEN has also shown that the parent compound reduces COC self-administration. Moreover, PHEN does not maintain self-administration and produces only limited positive subjective effects compared to d-amphetamine in COC users, which suggests that its abuse potential is low. Although PHEN has yet to be tested as a potential pharmacotherapy for COC dependence in human laboratory experiments or clinical trials to our knowledge, the results of extant preclinical experiments suggest it is a viable option.

In an ongoing study, we have demonstrated that COC can be safely administered to patients maintained on 70, 140 and 210 mg PHEN/day. Whether PHEN attenuates the reinforcing effects of COC, the best predictor for treatment efficacy (Comer et al., 2008; Haney and Spearman, 2008), remains to be determined. **The specific aim of this study is to demonstrate that PHEN maintenance reduces the reinforcing effects of intranasal COC.** To accomplish this aim, we will conduct an experiment in which non-treatment seeking COC-using participants (N=36) will be maintained on doses of PHEN (0 and 210 mg/day [target dose, dose will be titrated up as described below]). The reinforcing and other behavioral effects of intranasal COC (0 [placebo], 20, 40 and 80 mg) will be determined after 7 days of maintenance on the target PHEN dose (i.e., 210 mg/day). In order to monitor the safety of the drug combinations, cardiovascular measures will be taken routinely throughout experimental sessions and subjects will complete a daily side effect scale with nursing staff. We hypothesize that PHEN will attenuate the reinforcing effects of COC, as well as other abuse-related effects of COC (i.e., positive subjective effects). We also hypothesize that COC will be well tolerated during active PHEN maintenance.

## **2. OBJECTIVES**

The primary objective of this study is to determine the reinforcing effects of COC during maintenance on PHEN. We will also include a battery of subjective, performance and cardiovascular measures to more fully characterize the influence of PHEN maintenance on the effects of COC.

## **3. STUDY DESIGN**

A double-blind, placebo-controlled, crossover design will be used in this experiment. A completely within-subject design will be used such that each subject will receive all possible dose conditions, including placebo.

## **4. STUDY POPULATION**

Up to 100 individuals will be screened to participate in this study. We intend to enroll thirty six (24 male and 12 female) completers into the study. These individuals must be English-speaking, English-reading subjects 18-55 years of age of varying ethnic backgrounds and they will be recruited to participate in this five-week experiment. Enrollment in this study will occur between September 1, 2015 and August 31, 2016. Subjects will be required to provide legal proof of age. Subjects must be healthy and without contraindications to COC and PHEN. Subjects must also report recent use of COC and must meet diagnostic criteria for COC abuse or dependence using the Structured Clinical Interview for DSM-IV (SCID). Subjects must provide a COC positive urine during screening to verify COC use status. Screening procedures for all subjects will include a medical history questionnaire, laboratory chemistries (blood chemistry screen, complete blood count, ECG and urinalysis) and a brief psychiatric examination. These procedures will be conducted under our lab's screening protocol (03-0509). Chemistry values and screening outcomes must be deemed normal. If chemistry values or screening outcomes fall outside normal ranges, a study physician must deem them clinically insignificant for a subject to be enrolled. An electrocardiogram must also be within normal limits. Any potential subject with a history of serious physical disease, current physical disease, impaired cardiovascular functioning, chronic obstructive pulmonary disease, history of seizure or current or past histories of serious psychiatric disorder that in the opinion of the study physician would interfere with study participation will be excluded from participation. Subjects with current or past histories of substance abuse or dependence that are deemed by the doctor to interfere with study completion will also be excluded from participation. Female subjects must be using an effective form of birth control (e.g., birth control pills, surgical sterilization, IUD, cervical cap with a spermicide, condoms or abstinence) in order to participate. A urine pregnancy test will be conducted before the start of each experimental session to ensure that female subjects do not continue in the study if pregnant. All study subjects will be judged by the study physician, [name] or [name], M.D. to be healthy.

During the initial screening process, potential subjects will be asked to provide a urine specimen that will be screened for the presence of amphetamine, benzodiazepines, barbiturates, COC, tetrahydrocannabinol (THC) and opiates. In order to participate in an experimental session, subjects must provide a urine negative for amphetamine, barbiturates, benzodiazepines and opiates on each day of their participation. Subjects will be allowed to continue if they test positive for COC, if it is determined that this drug was given in a recent session and it is likely that the result is positive due to experimental administration. [name] or [name] will be notified of COC-positive urines on experimental session days and sessions will only proceed if subjects pass the sobriety test and have vital signs within acceptable limits (see below). Subjects will be maintained on a caffeine free diet and will have to abstain from alcohol for the duration of their participation.

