## 7. RESEARCH PROCEDURES

*General Procedures.* Subjects that meet the inclusion criteria will participate as inpatients at the University of Kentucky CCTS Research Inpatient Unit (CRIU). Subjects will be discharged upon completion of the entire protocol.

This experiment will require each subject to participate for approximately five weeks. Experimental sessions will be conducted as outlined in Table 1 below. We would like to note that COC doses will both be given in random order, whereas order of PHEN dosing will be counterbalanced across subjects. We would also like to note that subjects may be maintained on a given PHEN condition for more than 11 days prior to session to avoid testing COC doses on weekends.

Day	Table 1. Experimental Procedures
1	Admission to the CRIU.
2	Practice Session.
3-17	Placebo maintenance. Placebo administered twice daily (0700 and 1900 hours).
14-17	Experimental Sessions. Reinforcing effects of intranasal COC (0 [placebo], 20, 40 and 80 mg) determined using progressive-ratio procedure.
18-32	PHEN maintenance. Administered in divided doses (0700 and 1900 hours). Subjects receive 35 mg twice daily for two days, then 70 mg twice daily for two days, then 105 mg twice daily for remainder of maintenance period.
29-32	Experimental Sessions. Reinforcing effects of intranasal COC (0 [placebo], 20, 40 and 80 mg) determined using progressive-ratio procedure.
33	Discharge

During their participation in the research protocol, subjects will not be allowed to leave the CRIU, nor will visitors be allowed, with the exception that subjects can leave for walks under clinical supervision and if approved by physicians. Research subjects will be allowed to make local telephone calls. After completing the research protocol, interested subjects will be offered a referral to an appropriate drug abuse treatment program.

All subjects will provide urine and expired air samples before and periodically during study participation. The presence of non-nicotine drugs of abuse or alcohol not administered experimentally in the research protocol will result in immediate termination from the research study.

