This experiment will consist of 1 practice session and 8 experimental sessions conducted according to the timeline in Table 1 (see above). After admission, subjects will be allowed to acclimate to the CRIU for two days before beginning the study. During this time, subjects will be maintained on a caffeine-free diet, receive instructions concerning the details of the daily research procedures and general rules of the inpatient research unit and complete a "practice" session to familiarize them with the experimental routine and tasks.

Each day after the practice session, subjects will be awakened at 0700 hours and will receive maintenance medication. Medications will not be administered if a subject's heart rate is  $\geq 100$  bpm, systolic pressure is  $\geq 150$  mmHg or diastolic pressure is  $\geq 100$  mmHg. In addition, the UKU side effects scale will be completed daily to monitor for the emergence of side effects.

Subjects will then be allowed to eat a standard, fat-free breakfast (cereal with skim milk, 2 pieces of toast with jam or jelly and 8 ounces of fruit juice). Tables 2 and 3 (below) outline the activities of maintenance and experimental sessions. The sampling of each session will begin at 0900 hours and will last approximately 1 hour. Self-administration phases will begin at 1330 hours and will last approximately 2 hours. Experimental measures will be completed as outlined in Tables 2 and 3 below. Medications will not be administered if a subject's heart rate is  $\geq 100$  bpm, systolic pressure is  $\geq 150$  mmHg or diastolic pressure is  $\geq 100$  mmHg or if clinically significant and/or prolonged ECG abnormalities are detected.

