All drugs will be administered under double-blind conditions and under medical supervision. Test doses of COC will be 0 (placebo), 20, 40 and 80 mg, administered in random order. These doses were chosen based on prior work and similar doses have safely been administered to human subjects (Oliveto et al., 1995; [name] et al., Ongoing Study; [name] et al., 2008; 2010; 2012a; 2012b; Van Dyke et al., 1978). The maintenance conditions will be placebo and 210 mg PHEN/day (target dose). Subjects will be maintained on these doses for at least seven days before beginning experimental sessions. The dose of PHEN was selected based on results of previous clinical research, as well as a recently completed and ongoing studies in our laboratory showing that this PHEN dose is well tolerated by COC users (Bolin et al., Under Review; [name] et al., Ongoing). Placebo capsules will contain only cornstarch, whereas placebo powder will contain only lactose. Both will be visually identical to the powder and capsules that contain active drug.

**Apparatus.** Behavioral testing will be conducted at the CRIU. Subjects will be tested using an individual Macintosh laptop computer that automates behavioral tasks.

**Modified Progressive-Ratio Procedures.** The reinforcing effects of intranasal COC, alone and during maintenance on PHEN doses will be assessed using a progressive-ratio procedure. The outcome measures for this procedure are the break point (i.e., last ratio completed) and number of drug doses ingested.

Testing of each dose of intranasal COC under the proposed modified progressive-ratio procedure involves two phases: 1) Sampling and 2) Self-Administration.

**Sampling Phase.** Participants will complete a Sampling Phase for each of the active intranasal COC conditions to acquaint them with the drug effects. During each Sampling Phase, participants will receive a single administration of intranasal COC (0 [placebo], 20, 40 or 80 mg). Before each Sampling Phase, participants will be instructed to attend to the effects of the intranasal drug because later that day they will be able to work to receive additional doses of the inhaled drug. Participants will complete the battery of subjective effects questionnaires and performance task 30 minutes before the sampling dose of intranasal COC, immediately following and at 15-min intervals for 60 minutes. Cardiovascular measures will also be recorded at these times.

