## **10. SAFETY PRECAUTIONS**

Subjects are carefully screened (history and physical exam, routine labs such as CBC, complete metabolic panel and urinalysis, ECG and psychiatric assessment) to exclude those with potential increased risk of adverse effects, such as personal or first degree family histories of heart disease, histories of seizure or head injury associated with more than a brief loss of consciousness, hypertension, psychosis, etc. During sessions subjects remain under careful medical observation and

are monitored continuously by on-site medical staff. Vital signs will be collected throughout the dosing period. Staff is familiar with the acceptable physiological parameters for these studies and this information is posted in every experimental session room. In addition, [name] has substantial experience administering medications to human subjects under a variety of dosing conditions. Lastly, female subjects are also given pregnancy tests prior to each session to ensure that we do not administer active medications to a pregnant woman.

**Legal risks including loss of confidentiality:** All intake documentation that contains personal information is handled separately from the actual data collected during the study. All information of a personal nature (intake assessments, medical test results) is kept locked either on password-protected computers or in secure filing cabinets all behind locked doors and accessible only to key personnel involved in the research. A Certificate of Confidentiality will be obtained from NIDA.

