## **13. RESEARCH MATERIALS, RECORDS AND PRIVACY**

Urine and blood samples will be collected at screening prior to a subject's participation in the experimental protocol under another IRB approved protocol (Number 03-0509). These urine samples will be tested for the presence of a full range of drugs of abuse. Blood samples will be used for the laboratory chemistries. Females will also be given a pregnancy test at the time of screening (via the urine sample). Urine drug and pregnancy tests will be conducted prior to the conduct of each experimental session. Other data obtained from the subjects will involve subjective effects based on questionnaires, various computer-based tasks and non-intrusive staff observations and ratings. The consent form states that subject's confidentiality will be protected.

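### Required on-study pregnancy tests are tied to experimental sessions, so a woman assigned PHEN first can take at least 11 days of active drug with no test since screening

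*Combined protocol and SAP*

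**What the plan says.** Three sections of the combined protocol and SAP set the timing of on-study pregnancy tests.

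- Section 4 (Study Population): "A urine pregnancy test will be conducted before the start of each experimental session to ensure that female subjects do not continue" if pregnant.
- Section 13 (Research Materials, Records and Privacy): "Urine drug and pregnancy tests will be conducted prior to the conduct of each experimental session". The same section adds one urine pregnancy test at screening.
- Section 10 (Safety Precautions): "female subjects are also given pregnancy tests prior to each session to ensure that we do not administer active medications to a pregnant woman". The type of session is not named.

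Section 7 (Research Procedures) sets the calendar. It describes "1 practice session and 8 experimental sessions conducted according to the timeline in Table 1", so the practice session is counted apart from the experimental ones. Elsewhere it says that two of its tables "outline the activities of maintenance and experimental sessions", which is a wider use of the word. On dosing it says: "Each day after the practice session, subjects will be awakened at 0700 hours and will receive maintenance medication". Table 1 puts the practice session on day 2, the first maintenance block on days 3 to 17 with experimental sessions on days 14 to 17, and the second block on days 18 to 32 with sessions on days 29 to 32. It displays placebo first, but the text above it says that PHEN order is counterbalanced.

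**The concern.** Section 10 gives the purpose of the tests: active medication should not reach a pregnant woman. Section 17 makes not being pregnant a condition of participation. Under the rule in Sections 4 and 13, that condition is checked at screening and then not again until the first experimental session. In the order shown in Table 1 this does no harm, because the first block is placebo. In the reverse order the first block is active PHEN, and most of it is taken before the first explicitly required on-study test.

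No other described step clearly fills the gap. The consent visit (Section 6) lists a sobriety test and a breath alcohol sample. On maintenance days (Section 7, Table 2), dosing depends on vital signs and the absence of sedation or withdrawal. The other urine checks in Sections 4 and 7 concern drugs of abuse.

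What is at stake is exposure of an early pregnancy to PHEN: one too early to detect at screening, or conceived between screening and admission. This document sets no limit on that interval. The primary outcome and its analysis are not involved.

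**Working it through.** **Inputs**

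- First maintenance day 3, first experimental session day 14; second block starts day 18, its sessions day 29 (Section 7, Table 1).
- Titration (Table 1): "Subjects receive 35 mg twice daily for two days, then 70 mg twice daily for two days, then 105 mg twice daily for remainder" of the period, that is 70, then 140, then 210 mg/day.
- Time on the maintenance dose before testing (Section 7): "Subjects will be maintained on these doses for at least seven days before beginning experimental sessions".
- Two doses a day, at 0700 and 1900 (Table 1).

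**1. The plan's own figure.** Section 7 allows more than 11 days on a condition before sessions, to avoid weekends, which implies a usual 11. Table 1 reproduces it:

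- First block: 14 − 3 = 11 days (days 3 to 13).
- Second block: 29 − 18 = 11 days (days 18 to 28).
- From the titration: 2 + 2 + 7 = 11 days.

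**2. PHEN first: active drug before the first explicitly required on-study test**

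- Doses: 11 × 2 = 22, of which 7 × 2 = 14 are at the target dose.
- Amount: 2 × 70 + 2 × 140 + 7 × 210 = 140 + 280 + 1,470 = 1,890 mg.

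**3. Share of the full 15-day block**

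- Doses: 15 × 2 = 30; 22/30 = 73%.
- Amount: 2 × 70 + 2 × 140 + 11 × 210 = 140 + 280 + 2,310 = 2,730 mg; 1,890/2,730 = 69%.

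**4. How far these figures can move**

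- Table 3 gives the 0700 dose before the session starts at 0900. If the day 14 test follows that dose, the count is 22 + 1 = 23 doses and 1,890 + 105 = 1,995 mg.
- Each day by which sessions are put off to avoid a weekend adds 2 doses and 210 mg.
- Individual doses can be withheld for vital signs, so these are scheduled amounts.

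**5. PHEN second.** Tests are required before the sessions on days 14 to 17, and the first PHEN dose is on day 18. This sequence does not have the gap.

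**6. Reading Section 10 against Sections 4 and 13.** If each session in Section 10 includes the practice session, a test falls on day 2, one day before the first dose, and the untested time on study is zero. If it means experimental sessions, as Sections 4 and 13 say, it is at least 11 days. The surrounding text in Section 10 deals with the dosing period and with experimental session rooms, which favours the narrower reading without settling it.

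**The case against.** The strongest reply is that Section 10 already covers the point. It is the safety section, it requires a test before each session, and the practice session on day 2 is called a session. Read that way, all three sections can be satisfied together and only the wording is inconsistent. Sections 4 and 13 also do not say that tests are done at no other time. This reading is possible. It does not close the gap, because both sections that name the type of session limit it to experimental ones and no test on days 1 to 3 is named anywhere. Staff who followed Sections 4 and 13 to the letter would comply and still miss the aim stated in Section 10.

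Second, the tables are not complete schedules. Table 3 omits the pregnancy test and the urine drug test that the text requires on experimental days. That is correct, so the absence of a test from Tables 1 and 2 is weak evidence on its own. The point rests on the wording of Sections 4 and 13.

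Third, Section 7 says that urine is collected before and during participation, and screening is governed by a separate protocol (03-0509). Section 7 does not mention pregnancy in that context. The screening protocol is not available here; a short screening window or a repeat test in it would shrink the gap.

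Fourth, the risk is low. Contraception is required, there is a screening test, and subjects are confined without visitors, which makes conception during the 11 days implausible. All of this stands. It does not cover a pregnancy missed at screening or conceived before admission, and the accepted contraception includes condoms and abstinence.

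**Conclusion.** The concern holds. Under Sections 4 and 13, a woman assigned PHEN first can take at least 11 days of active PHEN, including 7 at the 210 mg/day target, with no required pregnancy test since screening.

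This rests on two assumptions: that experimental session has the meaning Section 7 gives it when it counts the practice session separately, and that the unseen screening protocol adds no test close to admission. The figures measure scheduled dosing without a test, not the risk of pregnancy. The number of pregnant women exposed cannot be derived from the documents, and the 12 women in Section 4 are a target for completers, not a count of women dosed.

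This should be fixed, because the plan's own safeguard is not secured in one of the two sequences and the remedy is cheap. Confidence is medium, given the ambiguity in Section 10.

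**What to change.** Require a negative urine pregnancy test at admission, or at the latest before the first maintenance dose on day 3, in addition to the tests before each experimental session. Apply it to every woman whichever sequence she is assigned, so that the test does not reveal the order of treatment. Use one identical statement of the testing times in Sections 4, 10 and 13, and add the test to Table 1.

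This brings the active PHEN days taken with no on-study test from at least 11 down to 0. It costs one extra urine test per woman and a short wording amendment. Section 7 already provides for urine samples before participation, so the added burden is small.
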